Specific Aim 1: Investigate the feasibility and tolerability of using rTMS on chronic pain in patients with opioid use disorder currently on methadone maintenance therapy and to investigate the effect of rTMS on chronic pain relief and substance use in an exploratory manner. Previous studies indicate that deep brain stimulation of the prefrontal cortex/anterior cingulate induces pain relief. Our hypothesis is that active rTMS, compared to sham, will improve pain after five weeks of treatment, thereby improving functional capacity and reducing opioid and other substance use.

Specific Aim 2: Investigation of the effect of rTMS using imaging. We will investigate target engagement with brain imaging. Magnetic resonance spectroscopy (MRS) will be used to measure changes in glutamate and vMRI to gauge changes in volume. Our hypothesis is that active rTMS will decrease glutamate levels and increase brain volume of the mPFC and ACC compared to sham.

Specific Aim 3: Investigation of the effect of rTMS on cognitive (i.e. executive) functioning in patients with chronic pain and opioid use disorder on methadone maintenance therapy. Previous studies have implicated a broad range of cognitive deficits in patients with substance use disorders, both during intoxication and withdrawal and after prolonged abstinence. Neuropsychological testing completed before and after rTMS treatment will be completed to determine if rTMS improves cognitive functioning, which may be a possible mechanism for improvement in chronic pain and/or opioid use disorder.

Background and Rational

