Participants may reduce or stop using opioids through the duration of the study. Reduced opioid use may result in reduced tolerance to opioids, which increases the risk of opioid overdose if a participant resumes opioid use at the same or greater quantity and/or frequency. Participants will be informed that reduced or discontinued opioid use will result in reduced tolerance and increased risk of overdose if opioids are resumed at the same or greater quantity and/or frequency. In addition to this counseling, participants will be offered an overdose reversal kit with intranasal naloxone (which are provided by the New York City Department of Health and Mental Hygiene and stored at our outpatient research clinic STARS and offered to any participant using illicit opioids and/or participating in an opioid treatment research study). However, since we do not anticipate reductions in their methadone dose, and participants will continue to engage in normal methadone program treatment, including drug counseling, participants will be at lower risk for overdose than patients with OUD who are not on agonist replacement therapy in the community.

3. rTMS.

The main risks of rTMS are as follows:

a. Seizure: This is the greatest concern with rTMS treatment. The incidence of rTMS-induced seizures worldwide is low and roughly comparable to the estimated incidence of spontaneous seizures with antidepressant therapy (0.1–0.6 %). In addition, rTMS-induced seizures are likely to occur during or just after the rTMS treatment session (rather than after a delay) while our subjects will be under observation. In addition, there have been no reports of epilepsy or repeated spontaneous seizures occurring due to after rTMS. Since the advent of the 1998 safety guidelines, we are aware of only 8 reports of rTMS-associated seizures, and six involved either stimulus parameters exceeding the safety guidelines, or included concomitant medication or sleep deprivation, which lower the seizure threshold.

b. Lowering the Seizure Threshold: The use of concurrent medication has been implicated as a risk factor in some of the seizures reported with rTMS. These medications include tricyclic antidepressants and neuroleptics, which are not used in this study.

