In the event of a seizure, the following procedures will be employed. An MD will be in the building and immediately available during all rTMS sessions. The staff member with the subject will make sure that the participant is on the floor (cannot fall) and will clear the area of all objects. Most seizures will end spontaneously at 1 to 2 minutes. In the event that the seizure has not ended in two minutes, the hospital emergency team will be called and Lorazepam (which is stored in the room) will be administered IM (4mg). If seizures continue or recur after a ten to twelve minute observation period, an additional intravenous dose of 4 mg may be administered until the acute care medical team arrives.

Brainsway has performed studies using the TMS H-coil device in control subjects and subjects in clinical conditions, including major depressive disorder, schizophrenia, bipolar disorder, obsessive compulsive disorder, addiction, blepharospasm, Parkinson's disease, and post-traumatic stress disorder (PTSD) (Brainsway, Ltd., unpublished data). High frequency (10-20 Hz) and high intensity (<120% of motor threshold [MT]) rTMS have been administered to 209 subjects, who were treated with for a total of 3314 sessions and 143,514 pulse trains. 98 of the 209 subjects received rTMS treatments (1296 sessions, 54,432 pulse trains) without concomitant psychotropic medications (which may lower the seizure threshold) and none experienced a seizure. The remaining 111 subjects received rTMS (2018 sessions, 89,082 pulse trains) in addition to concomitant

medications that could affect seizure threshold. Three of these subjects had a seizure. Of these three, one was taking antidepressant medications (venlafaxine, mianserine, mirtazapine), another was taking medications for schizophrenia (olanzepine, citalopram and lorazepam) and the third was taking lithium and clonazepam for bipolar disorder.

The primary safety outcome will be the absence of a serious adverse event or an unresolved non-serious adverse event. For each subject, we will inquire about potential non-serious adverse events after each sessions of rTMS. We will ask about headache, hearing changes, jaw pain, and mood symptoms. If these events are reported by the subject, we will follow these daily until they remit.

The risk of pregnancy and rTMS are unknown therefore subjects who are pregnant will not be included in the study.

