c. Headache: A mild headache, which responding readily to non-opioid analgesics is the most common side-effect reported in depression treatment trials. All volunteers will be treated with NSAIDs as needed for headache.

d. Hearing Impairment: Rapid excitation of the stimulation coil produces clicks that have resulted in transient increase in the auditory threshold, which does not occur if earplugs are used. A previous study assessed the auditory threshold before and after 30 sessions of rTMS (over 6 weeks) in subjects wore earplugs during stimulation and no significant mean changes were detected. All participants will wear earplugs during the delivery of stimulation.

e. Additional risks include scalp pain, dental pain, and rTMS-induced manic effect. Subjects will be evaluated for each of these and treated with over the counter pain medications if required for the scalp and dental pain. Subjects will also be evaluated for an rTMS-induced manic effect. If mania occurs, they will be removed from the protocol and monitored until these symptoms resolve.

f. Additional risks include scalp pain and rTMS-induced manic effect. Subjects will be evaluated for each of these and treated with over the counter pain medications if required for the scalp and dental pain. Subjects will also be evaluated for an rTMS-induced manic effect. If mania occurs, they will be removed from the protocol and monitored until these symptoms resolve. Convulsive 14 syncope has also been reported, and we will take the following measures to prevent this: participants will be asked to immediately report any symptoms of syncope (e.g. feeling dizzy, light headed, visual changes) and will be placed in the supine position with elevated legs if syncopal symptoms appear.

5. Risks associated with the psychological test battery include potential nervousness and frustration with the tasks. A member of the research team will carefully explain the tests before hand and will be available for questions during the tasks should they arise.

Adverse Event Reporting

Timely, accurate, and complete reporting and analysis of safety information from clinical studies are crucial for the protection of subjects and investigators, and are mandated by regulatory agencies worldwide.

1. Adverse Event Definitions and Classifications

• Adverse Event

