An adverse event is any untoward medical occurrence in a clinical study subject. An adverse event does not necessarily have a causal relationship with the treatment. An adverse event can therefore be any unfavorable and unintended sign (including an abnormal finding), symptom, or disease temporally associated with the use of an investigational product, whether or not related to the investigational product. (Definition per International Conference on Harmonization [ICH])

This includes any occurrence that is new in onset or aggravated in severity or frequency from the baseline condition, or abnormal results of diagnostic procedures, including laboratory test abnormalities.

• Serious Adverse Event

A serious adverse event as defined by ICH is any untoward medical occurrence that meets any of the following conditions:

- Results in death
- Is life-threatening
- Requires inpatient hospitalization
- Results in persistent or significant disability/incapacity, or
- Is a congenital anomaly/birth defect

Note: Medical and scientific judgment should be exercised in deciding whether expedited reporting is also appropriate in situations other than those listed above. For example, important medical events may not be immediately life threatening or result in death or hospitalization but may jeopardize the subject or may require intervention to prevent one of the outcomes listed in the definition above. Any adverse event is considered a serious adverse event if it is associated with clinical signs or symptoms judged by investigator to have a significant clinical impact.

• Unlisted (Unexpected) Adverse Event

An unlisted adverse event, the nature or severity of which is not consistent with the applicable product information (e.g. Investigator's Brochure for an unapproved investigational product or the package insert/summary of product characteristics for an approval product) (ICH)

2. Adverse Event Classification

• Mild:

Signs or symptoms, usually transient, requiring no special treatment and generally not interfering with usual activities.

• Moderate:

Signs or symptoms that may be ameliorated by simple therapeutic measures yet may interfere with usual activities.

• Severe:

Signs or symptoms that are intense or debilitating and that interfere with usual activities. Recovery is usually aided by therapeutic measures.

3. Relationship to Investigational Device

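### The only safety or tolerability outcome scores a subject who stops rTMS for a non-serious event that later resolves as a success, and Aim 1 has no stopping or session-completion measure

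*Combined protocol and SAP*

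**What the plan says.** The safety outcome appears under *Risks associated with the study*, item 3 (rTMS): "The primary safety outcome will be the absence of a serious adverse event or an unresolved non-serious adverse event". Subjects are asked about headache, hearing changes, jaw pain and mood symptoms after each session, and "If these events are reported by the subject, we will follow these daily until they remit". No time point is attached to the word unresolved.

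Specific Aim 1 begins: "Investigate the feasibility and tolerability of using rTMS on chronic pain in patients with opioid use disorder". The *Statistical Analysis* section defines an effectiveness outcome and describes the pain analyses. It contains no analysis of adverse events, discontinuation or session completion.

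Some events require removal. Under item 3e, "If mania occurs, they will be removed from the protocol and monitored until these symptoms resolve". *Criteria for Early Discontinuation* removes subjects whose depressive symptoms worsen or whose HRSD exceeds 17.

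Under *Adverse Event Reporting*, section 1, an event is serious if it meets one of five listed conditions. A note adds that "important medical events may not be immediately life threatening or result in death or hospitalization" and may still warrant expedited reporting. A final clause makes any event serious if its signs or symptoms are "judged by investigator to have a significant clinical impact". Section 4 requires every adverse event to be recorded with its relatedness.

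On seizure, item 3a says "This is the greatest concern with rTMS treatment". The emergency procedure expects that "Most seizures will end spontaneously at 1 to 2 minutes".

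**The concern.** The outcome looks at how an event ended and how serious it was, and ignores what it did to treatment. Headache, scalp pain or jaw pain that drives a subject out of a five-week daily course, and then clears, leaves that subject scored the same as one who completed every session without complaint.

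This would matter less if tolerability were measured elsewhere, but it is not. The active arm could report 100% on its primary safety outcome although subjects left because of the stimulation, and a difference between active and sham in such departures would not appear in any planned summary. For a feasibility study that difference is part of the main answer. The sham is designed to reproduce the scalp sensation and facial-muscle activation of the active coil, so a by-arm comparison of stopping would be informative.

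**Working it through.** The conclusion rests on the text. The plan gives no sample size, safety threshold or expected stopping rate, so there is no figure of its own to reproduce.

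**Step 1: apply the definition.** A subject fails only with a serious event or a non-serious event that has not resolved.

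| Course of events | Primary safety outcome |
|---|---|
| Headache ends treatment, then resolves, not judged serious | Success |
| Mania, removed, monitored to resolution, not judged serious | Success |
| Depression worsens, removed, recovers, not judged serious | Success |
| Any of these judged to have significant clinical impact | Failure |
| Mild headache, treatment completed, still present at the end | Failure |

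The last row shows the ordering problem: a mild lingering complaint fails, while a resolved event that ended treatment passes.

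**Step 2: look for another measure that would catch the first three rows.** *Statistical Analysis*, *Post-treatment Follow-up* and *Adverse Event Reporting* define none. The planned exposure is 5 weeks × 5 days = 25 sessions, but completed sessions are not an outcome.

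**Step 3: when is unresolved judged?** Adverse events are collected to the last study-related procedure, and follow-up visits fall 2 and 4 weeks after completion of rTMS. That implies an end point for completers. Because the visits are timed from completion, a subject who stops early has no clearly assured 4-week visit.

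**Step 4: seizure.** A brief seizure without hospitalisation need not meet any of the five listed conditions, so its seriousness rests on the note and the clinical-impact clause. That judgement settles both the 24-hour report and the safety outcome. Mania, worsening depression and pregnancy require removal; no text stops rTMS after a seizure.

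**Step 5: illustration of size.** Assume an active arm of n subjects and a probability p of stopping for a resolved non-serious event. Both are assumptions. The chance of at least one such subject is 1 − (1 − p)^n; for example, 1 − 0.90^20 = 87.8%.

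| n (assumed) | p = 2% | p = 5% | p = 10% | p = 15% |
|---|---|---|---|---|
| 10 | 18.3% | 40.1% | 65.1% | 80.3% |
| 20 | 33.2% | 64.2% | 87.8% | 96.1% |
| 30 | 45.5% | 78.5% | 95.8% | 99.2% |

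The expected number at n = 20 is 20p, that is 0.4, 1, 2 and 3. At p = 10% and with no other failures, the outcome reads 20/20 (exact 95% CI 83.2–100%), while 18/20 (68.3–98.8%) had no such stop.

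**The case against.** The strongest reply is that a safety outcome is being faulted for not measuring tolerability. Serious-or-unresolved is a recognisable safety endpoint, and rewriting it to include every stop would be a matter of preference. It would also add noise, because removals for worsening depression unrelated to stimulation would count as safety failures in both arms. This stands, and it is why the remedy is a separate tolerability outcome.

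Second, the clinical-impact clause is broad. An investigator could use it to class a treatment-ending headache as serious, and would probably use it for mania or a seizure. This also stands: none of the cases is free of judgement. But nothing requires the upgrade, and stopping treatment is not itself a criterion.

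Third, the assumed stopping rates may be too high. Subjects with a motor threshold of 85% are removed before rTMS begins because of expected discomfort, intensity is ramped up over 2–3 days, and headache is described as mild and readily treated. These favour the low end of the table, and no figure there should be read as a forecast.

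A reader might also infer that these events go unseen. The documents do not support that: subjects are asked after every session, assessed by a psychiatrist at least weekly, and every event is recorded with relatedness. Nor is there a stated safety threshold, so no decision rule turns on the proportion.

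**Conclusion.** The concern holds for the outcome definition. As written, a subject whose treatment ended because of a non-serious event that resolved is a safety success unless the investigator upgrades the event, and no planned measure addresses the tolerability part of Aim 1. The size is unknown from the documents. Under an assumed 20 active subjects and stopping rates of 2–15%, between 0.4 and 3 subjects would be expected to be scored this way.

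Two stronger readings are not supported. One is that seizures would pass as successes: the text leaves a brief seizure to judgement, and a careful investigator would probably call it serious, so this is a secondary point of wording. The other is that the device's earlier seizure counts put a probability on that case. Those seizures occurred in subjects on concomitant medications that could affect seizure threshold. Exclusion 7 bars neuroleptics and any drug known to raise seizure risk, so it would keep out many such subjects, and the counts do not carry over to this population.

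**What to change.** Keep the primary safety outcome and add that resolution is judged at the subject's last study visit, which also covers those who stop early.

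Add to *Statistical Analysis*: *Tolerability will be reported by arm as the number and proportion of subjects with an adverse event, resolved or not, leading to a permanent stop of rTMS or removal from the study, overall and by investigator-assessed relatedness, together with the number of sessions completed out of 25.* The split by relatedness separates removals such as worsening depression that the investigator does not attribute to stimulation.

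As a secondary clarification, add to the serious adverse event definition: *Any seizure is a serious adverse event.* Add to *Criteria for Early Discontinuation*: *rTMS stops in any subject who has a seizure.*

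The cost is one CRF field for the reason rTMS stopped and a few sentences of text. No new visit is needed, and adverse events and relatedness are already collected. The tolerability figure will look less favourable than the safety proportion alone.
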